Most accepted therapies for PAH have been aimed at vasodilation of the pulmonary vasculature, and there has been little thought that PAH patients would benefit from traditional left heart failure treatments. A cornerstone therapy in left heart failure is β -adrenergic receptor blockade because of its ability to reverse cardiac remodeling and improve clinical outcomes, despite decades of concern regarding its propensity to exacerbate heart failure. It has been reported to reduce mortality by about 30% in patients, and while the precise mechanisms that contribute to its beneficial effects remain to be elucidated, there is evidence that patients with underlying contractile reserve (*i.e.*, via recruitment of viable myocardium with β -adrenergic receptor stimulation) may experience greater recovery of their cardiac function. The current treatment recommendations regarding the use of β blockers in pulmonary hypertension state that there are possible unfavorable consequences on hemodynamics and functional exercise capacity, particularly when a relatively diminished and fixed stroke volume can be compromised. With a decreased stroke volume and an inability to increase it, patients with PAH depend on their heart rate response to increase cardiac output during exercise. In patients with severe mitral stenosis and pulmonary hypertension undergoing valvuloplasty, intravenous administration of atenolol was associated with further increase in pulmonary vascular resistance due to reduction in cardiac output. These observations have led to the belief that β -adrenergic blockers are detrimental in patients with PAH. This was supported by a small study of 10 patients with portopulmonary hypertension, in whom withdrawal of propranolol was associated with an increased exercise tolerance. However, only the β -blockers metoprolol and carvedilol have FDA approval for the treatment of left heart failure, and many studies have shown that the negative short-term effects such as fatigue and decreased exercise capacity of β blockade are overcome by a reversal of unfavorable cardiac remodeling. In a study using rats with pulmonary hypertension treated with β blocker, RV function improved, and maladaptive myocardial remodeling was prevented. Hence, in the same manner, in patients with PAH who are not destabilized and have preserved cardiac output and hemodynamics, the true short-term risks versus long-term benefits on reducing progressive RV dysfunction remained untested.

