Safety monitoring parameters will be collected via daily and/or weekly phone calls and at all follow-up visits. Subjects will be asked whether they have experienced any side effects and to describe these symptoms and to provide the BP and heart rate home records, which will be recorded in the electronic medical record. We will also monitor subjects throughout their enrollment and record whether there have been any deaths or hospitalizations during the study.

Compliance

Subjects will be asked to bring the study medication and bottles with them to each follow-up visit. A tablet count will be performed to estimate compliance. Subjects will also be asked how many tablets per day they have been taking on average, and how many times a week they miss a dose.

H. Early Withdrawal

Patients may be withdrawn from the study for any of the following reasons:

- Pregnancy
- Lung transplantation
- Unacceptable side effects or toxicity, as deemed by the principal investigator
- Patient non-adherence or inability to communicate with the patient
- More than three dose reductions of medications required
- Patient request to withdraw from the study

I. Data Monitoring

a. Quality Control

Data will be monitored for quality control by the study coordinator, statistician and principal investigator. Within the study database, conventional limits will be set on each data entry cell to minimize entry of erroneous values.

b. Recruitment

Problems with recruitment will be assessed after 12 months of enrollment of the first patient. If less than a fourth of the sample size has been recruited for the study, additional recruitment strategies will be addressed and implemented.

c. Benefit/Risk and Subject Safety

This study will be submitted to the Institutional Review Board for review of the benefits and risks of the proposed trial. We plan to comprise a Data and Safety Monitoring committee to oversight

the trial. Overall, we believe the potential benefits of carvedilol for PAH outweigh the potential risks of the study.

Potential Benefits

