Risks Associated with Blood Draws and Genetic Risks

Risks associated with blood draws include brief pain resembling a bee sting, light bruising, bleeding, swelling, lightheadedness, and very rarely, infection. Although not a part of the longitudinal trial, in anticipation of future analyses of relationships of outcome parameters to hereditary PAH, DNA will be extracted from blood cells for genetic analyses of mutations in the genes associated with PAH, such as BMPR2. Work with the DNA will be performed at Cleveland Clinic by our collaborator [name]. Genetic samples will only be identified by an ID number (not the patient name), and no genetic analyses will be performed other than that associated with PAH. Any identifying data will be kept in a locked drawer. The laboratory processing the DNA is a research facility. Genetic information about the patient or other information obtained from the blood sample will not be given to the patient, family or the patient's doctor. The patient may withdraw consent to use of the blood at any time by contacting the PI of the study.

Data and Safety Monitoring

This is a small, single-center trial, mechanistic study but will be registered on ClinicalTrials.gov. An internal Data Safety Monitoring committee will be comprised of Cleveland Clinic physicians who are experts in heart failure, β -blocker therapy, functional assessment of the heart, and

pulmonary hypertension: [name], Chair of the DSM committee, and members including [name], and [name]. [name], biostatistician will also serve on the committee for purposes of data analyses and quality control. Participant safety will be protected and monitored by weekly phone calls to the patients and biweekly review of the safety and tolerability outcome measures by the study coordinator. These safety and tolerability outcomes and any other adverse events that occur will be recorded in the patient's electronic medical record. Any adverse events that occur will be investigated to identify possible etiology and relationship to study procedures and reported to the IRB and the DSM committee within 10 working days of their discovery, with the exception of any deaths, which will be reported within 5 working days of their discovery.

d. Early Termination

Because this study requires a small sample size, there are no mid-study analyses scheduled, and thus a plan for early termination is not necessary.

G. Data Analysis/Reporting

a. Analysis Plan

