Baseline characteristics will be reported, including age range and the proportions that are female, postmenopausal, and Caucasian. Means and standard deviations or medians and interquartile range will be reported for all continuous data, and non-continuous data will be reported as percentages. A log transformation may be utilized for any data that is not normally distributed. The three randomized study groups will be compared, based on the intent-to-treat principle, with respect to changes from baseline. Repeated measures analysis of variance will be used to compare groups using data from all time points together, though T-tests will also be used to compare pairs of groups with respect to differences between pairs of time points. Using actual administered doses, relationships between dose and changes over time will also be explored using appropriate linear or non-linear models to estimate dose-response relationships. Reports of blinded group summaries of adverse events will be regularly produced for safety monitoring.

b. Confidentiality

To maintain patient confidentiality, all study data will be de-identified. Each subject, upon enrolling in the study, will be assigned a three-digit subject number. Case report forms and the study database will identify each subject only by subject number and will contain no patient identifiers. De-identified case report forms will be kept within study binders, kept in a locked filing cabinet in a locked room. Completely de-identified study data will be stored in a data table maintained on a password-protected computer and stored on the Cleveland Clinic network, which is regularly backed up. The code identifying which patient belongs to each subject number will be kept in a separate locked filing cabinet in a locked room. Only the study coordinator and investigators will have access to this code.

REFERENCES

1. ATS statement: guidelines for the six-minute walk test. Am J Respir Crit Care Med 2002;166:111-7.

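### Small size and the lack of an interim analysis do not remove the need for a harm plan: no trial-level review of events by arm, and no committee role in pausing or stopping, is described

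*Combined protocol and SAP*

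**What the plan says.** The Early Termination paragraph (I. Data Monitoring, d) is a single sentence. It gives the small sample size as its reason and states that "there are no mid-study analyses scheduled, and thus a plan for early termination is not necessary".

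The Analysis Plan (G. Data Analysis/Reporting, a) describes one aggregate safety output: "Reports of blinded group summaries of adverse events will be regularly produced for safety monitoring". It does not say how often, to whom, or whether the summaries are pooled or split by coded arm.

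Oversight appears in two places. Benefit/Risk and Subject Safety says "We plan to comprise a Data and Safety Monitoring committee to oversight" the trial. Data and Safety Monitoring adds that "An internal Data Safety Monitoring committee will be comprised of Cleveland Clinic physicians who are experts in heart failure" and related fields, and that a "biostatistician will also serve on the committee for purposes of data analyses and quality control". Adverse events go to the IRB and the committee within 10 working days, and deaths within 5. Patients are telephoned weekly, and the study coordinator reviews safety outcomes every two weeks.

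The background reports current treatment recommendations as saying, of beta-blockers in pulmonary hypertension, that "there are possible unfavorable consequences on hemodynamics and functional exercise capacity". The sponsor's own view is stated under Benefit/Risk: "Overall, we believe the potential benefits of carvedilol for PAH outweigh the potential risks of the study".

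**The concern.** The Early Termination sentence draws a conclusion that its premise does not carry. Having no scheduled mid-study analysis explains why there is no rule for stopping on efficacy. It says nothing about what happens if deaths or heart-failure admissions accumulate in one arm. This is a stated decision, so it cannot be put down to missing or redacted text.

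The treatment recommendations cited in the background are the reason it matters. The background also says that the balance of short-term risk and long-term benefit is untested. The run-in covers one week at 3.125 mg twice daily, while the escalation arm may reach 25 mg twice daily after randomization, which is 25 / 3.125 = 8 times the dose tested in run-in. A harm signal specific to that arm could therefore arise only after randomization, and would show only in a comparison of arms.

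**Working it through.** **1. What the described safeguards can see**

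| Safeguard | Where | Acts on | Compares arms? |
|---|---|---|---|
| Monitored first dose, one-week run-in | Study Design; Open-label Run-in Phase | One patient, before randomization | No |
| Dose reduction, then removal from drug | Double-blinded Randomized Phase; Blinded Medication Dispensing | One patient | No |
| Withdrawal for toxicity | H. Early Withdrawal | One patient | No |
| Event reports in 10 working days (deaths 5) | Data and Safety Monitoring | One event | Not stated |
| Biweekly coordinator review | Data and Safety Monitoring | Safety outcomes | Not stated |
| Blinded group summaries | Analysis Plan | Aggregate | Only if coded by arm |

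No row leads from an excess in one arm to a decision about the trial. No meeting schedule, access to assignments, or authority to pause or stop is given for the committee. The research pharmacist is the only person described as knowing assignments.

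**2. Arm size, reproduced from the plan**

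Sample Size Rationale: 14 per group; 14 / 0.90 = 15.6, so 16 per arm; 16 × 3 = 48 randomized; 48 / 0.70 = 68.6, against the stated 68. The allocation ratio is not stated; I assume it is equal. Half of randomization is then 8 per arm.

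**3. Is arm-level review futile at this size? (illustration)**

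The documents give no serious-event rates, so every rate below is an assumption. I also assume complete follow-up on 8 patients per arm, which is generous given 24 weeks of treatment and recruitment as patients become available.

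Illustrative prompt: Beta(0.5, 0.5) prior on each arm's event rate; flag a carvedilol arm if P(its rate > placebo rate | data) > 0.95. With x events in 8, the posterior is Beta(x + 0.5, 8 − x + 0.5).

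- 3 versus 0: 0.979 (flags)
- 2 versus 0: 0.938 (does not flag)
- 4 versus 1: 0.949 (does not flag)

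The chance of a flag is the sum of the binomial probabilities over all flagged outcomes. Across both arms it allows for the shared placebo arm, with both carvedilol arms at the same rate.

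| Carvedilol vs placebo rate | One arm | Either arm |
|---|---|---|
| 5% vs 5% | 0.4% | 0.8% |
| 10% vs 10% | 1.7% | 3.3% |
| 20% vs 5% | 14% | 25% |
| 30% vs 5% | 31% | 49% |
| 40% vs 5% | 51% | 69% |

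For comparison, a two-sided Fisher test at 0.05, pooled carvedilol against placebo, for 20% versus 5%, has 0.5% power at half enrolment (16 vs 8) and 15% at full enrolment (32 vs 16). A count prompt of 3 or more events in the first 16 carvedilol patients is reached with probability 4.3% at a true rate of 5% and 64.8% at 20%, but also 21% at 10%, so it depends on knowing the background rate.

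Formal interim testing would be nearly powerless. A prompt for review rarely fires falsely in the equal-rate cases above and catches large excesses about a third to half of the time per arm. None of these thresholds is a recommendation.

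**The case against.** The strongest defence is that much safety oversight is already in place. Physicians expert in heart failure, beta-blockade and pulmonary hypertension receive every adverse event on a deadline, and a biostatistician sits with them. Hospitalization for heart failure already leads to dose reduction in any arm. This stands: a reader might infer that harm would run unchecked, and the documents do not support that.

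Three other strong readings also fail.

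- A reader might infer that the safety reports are bound to conceal an imbalance. The phrase about blinded groups could mean summaries coded A/B/C, which would show an imbalance without naming the arm. Only pooled summaries would hide it, and the text does not say which is meant.
- A reader might infer that the plan forbids stopping. The sentence can be read as covering formal interim analysis only. It does not remove IRB or committee authority, and blinding is stated for subjects and investigators, not for the committee.
- A reader might infer that the sponsor regards the drug class as unfavorable. That concern is attributed to treatment recommendations; the sponsor judges benefits to outweigh risks.

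The defence may add that 48 randomized patients are too few for a useful interim comparison. In part this stands: the illustrative prompt misses a fourfold excess (20% vs 5%) in a given arm about 86% of the time. That argues against a formal boundary. It does not argue against letting the committee see events by arm, since expert judgement can weigh a few serious cases that no test would call significant.

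**Conclusion.** The point holds in a limited form. The inference from small size and no mid-study analysis to no need for an early-termination plan is sound for efficacy and unsound for harm. The documents describe no trial-level review of events by arm and no committee role in pausing or stopping. Whether the summaries would reveal an imbalance cannot be settled from the text.

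The practical size of the gap is unknown, because no event rates are given. The illustration shows only that review by arm is workable at this size. It rests on assumed rates, equal allocation and complete follow-up, and its sensitivity to moderate harm is modest. It supports a non-binding prompt and not a numerical stopping rule. This is an inexpensive safety improvement that the sponsor should make; it does not undermine the efficacy design.

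**What to change.** Replace the Early Termination sentence with:

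> No efficacy interim analysis is planned. The DSM committee will review deaths, hospitalizations and serious adverse events by treatment arm at stated intervals, in closed reports prepared by the unblinded pharmacist or a statistician not involved in the final analysis. It may recommend pausing or stopping the trial or an arm for harm, under a non-binding guideline that the committee sets in advance. Investigators and the trial analyst stay blinded.

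The sponsor needs to fill in the intervals, since the Analysis Plan says only that reports are regular. The Analysis Plan should also say whether its blinded group summaries are pooled or coded by arm, and who receives them. The separate report-writer matters because the plan names a statistician under Quality Control and a biostatistician on the committee, and the reader cannot tell whether they are the same person. The committee, not this review, should choose any threshold.

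The cost is one paragraph, a short charter and an occasional false alarm that prompts a review. A review for harm only, with no option to stop for efficacy, spends no efficacy type I error.

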Target enrollment for this study will be 68 patients. The primary outcomes FDG-PET uptake and erythropoietin, are anticipated to have positively skewed distributions, amenable to the use of ratios of 6-month measures relative to baseline to measure changes over time. Log transformed ratios are then anticipated to have approximately normal distributions. For secondary measures demonstrating less skewness or even approximate normality without the log transformation, absolute changes from baseline to 6 months will be used to measure change over time. Sample size is determined taking into account the power of the T-test for comparing the placebo and low dose carvedilol groups with respect to the reduction in FDG-PET uptake, as measured by the ratio of 6-month uptake to baseline uptake. Variability in FDG-uptake measures over 6 months suggests an expectation that the coefficient of variation in uptake ratios will not exceed 50%. Using a Bonferroni correction to adjust for multiple time points with $\alpha=0.025$, the T-test comparing log-ratios has 90% power to detect a difference in groups such that ratios have a 50% lower median for the low dose carvedilol group relative to the placebo group, if the groups contain $n=14$ subjects each. This effect size was selected based on previously observed reductions in FDG-PET uptake of roughly 50% among patients on β -blocker. Considering 10% potential dropout after randomization and a 30% potential dropout during the run-in phase, we intend to enroll 68 patients into the run-in phases, to achieve at least 48 patients eligible for randomization into the placebo, low dose Carvedilol, or dose escalation groups.

D. Enrollment

Recruitment Strategy

Patients who are diagnosed with PAH will be identified as potential subjects by either a nurse or doctor involved in the patient's disease management. These patients will be referred to the study investigators for screening and to obtain informed consent. Subjects will be recruited as they become available and without regard to gender, race, or ethnicity.

Informed Consent

All volunteers will be approached by the study investigators or their designee. The consent interview will take place the day of a patient visit to the Pulmonary Department. In a private examination room, one of the research investigators will explain the details of the study, to the

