Doppler echocardiography will be performed by a single well-experienced echo technologist ([name]) for all studies to estimate PAP, RV and LV function using previously validated methods. Right ventricular function will be assessed via measurement of RV fractional area change (RVFAC), RV ejection fraction, myocardial performance index (MPI) of the RV, tricuspid annular plane systolic excursion (TAPSE), tissue Doppler-derived systolic velocity of the lateral tricuspid annulus (S' velocity), three-dimensional RV ejection fraction, and longitudinal strain and strain rate with tissue Doppler techniques (conventional technique, 2-dimensional speckle tracking and velocity vector imaging). Among these methods, the most used parameters are RVFAC, TAPSE, S' velocity of the lateral tricuspid annulus, and RV MPI.

Exhaled NO measurement

The participant will take in a deep breath and exhale through a mouthpiece attached to the nitric oxide analyzer (Aerocrine). This will be repeated for a total of three exhaled NO readings. NO is measured using the American Thoracic Society recommended guidelines.

FDG-PET scan

Cardiac-gated fasting FDG-PET scans will be conducted on fasting patients at baseline and 6 months. Finger stick blood sugar will be measured to assure fasting state (blood sugar < 120 mg/dl). Patient data will be acquired using a clinical PET/CT scanner (Biograph mCT 128) having time-of-flight capable PET detectors. First, a low-dose CT scan will be acquired to provide an attenuation map for PET data corrections. Then, a PET scan will be acquired in list mode for fifteen minutes with ECG signals obtained during the scan. Both static and gated images will be reconstructed using advanced iterative algorithms available on the scanner. All subjects will be fasting 8 h prior to and during the study, then injected with 370 MBq (10 mCi) FDG and scan performed at 1.5 h post-injection. Images will be analyzed in a blinded fashion by [name] using an image fusion workstation (MSViewer, CPS Innovations, Knoxville, TN) with region-of-interest (ROI) measuring tools. A total of five ROI will be measured in heart (left & right atria, RV, LV and IVS). In addition, ROI will be measured for the blood pool of the thoracic aorta. FDG uptake depends on factors including time between injection and scan, blood glucose, and body mass. For consistency, relative uptake will be normalized to blood pool FDG in thoracic aorta.

Safety and tolerability outcomes

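### The co-primary endpoints are compared on change from baseline without adjusting for the baseline value; ANCOVA on log baseline would probably gain precision from data already collected, for one degree of freedom.

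*Combined protocol and SAP*

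**What the plan says.** Section G, Data Analysis/Reporting, a. Analysis Plan: "The three randomized study groups will be compared, based on the intent-to-treat principle, with respect to changes from baseline". The methods are a repeated measures ANOVA over all time points, and "T-tests will also be used to compare pairs of groups with respect to differences between pairs of time points".

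Section C, Sample Size Rationale and Estimate, sizes the trial on the reduction in FDG-PET uptake "as measured by the ratio of 6-month uptake to baseline uptake". It sets the log scale for both co-primaries, FDG-PET uptake and erythropoietin: "Log transformed ratios are then anticipated to have approximately normal distributions". It then states that "the T-test comparing log-ratios has 90% power to detect a difference in groups" with 14 per group, where "ratios have a 50% lower median for the low dose carvedilol group relative to the placebo group".

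On timing, the FDG-PET scan section says: "Cardiac-gated fasting FDG-PET scans will be conducted on fasting patients at baseline and 6 months". Table 1 has erythropoietin at baseline and at months 3 and 6. Section D lists both among the baseline procedures, ahead of the open-label run-in and randomization.

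No section names the baseline value, or any other variable, as a covariate.

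**The concern.** The log of the 6-month/baseline ratio is ln(6-month) minus ln(baseline). Comparing arms on it forces the slope on baseline to be exactly 1. When the correlation between the two measurements is well below 1 and the variances are similar, that slope is too steep, and subtracting baseline adds noise to the comparison. ANCOVA estimates the slope instead.

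The repeated measures ANOVA does not supply the adjustment for FDG-PET. With only two time points, its group-by-time test is the same change-score comparison.

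There is little slack. The 48 randomized patients, less 10% dropout, over three equal arms leave 48 × 0.9 / 3 = 14.4 per arm, against the 14 assumed. Chance imbalance is also likely: with 14 per arm, the baseline difference between two arms has a standard error of √(2/14) = 0.38 baseline SD. If the true effect is smaller than planned, the unused precision could decide whether it is detected.

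**Working it through.** **Inputs from Section C.** n = 14 per arm; alpha 0.025 (sidedness not stated, two-sided assumed); coefficient of variation of the uptake ratio at most 50%; 50% lower median, so δ = ln 2 = 0.693.

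**Inputs assumed.** ρ, the correlation of log baseline with log 6-month value, is not given; I use 0.3 to 0.9. A 40% reduction, δ = −ln 0.6 = 0.511, is added to show a smaller effect. Log variances are first taken as equal at both times.

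**1. The plan's own figure.**
- SD of the log ratio = √ln(1 + 0.5²) = 0.472.
- SE of the difference = 0.472 × √(2/14) = 0.1785.
- Noncentrality = 0.693 / 0.1785 = 3.88 on 26 df, giving power of 92.6%.
- Using 0.5 directly as the log SD gives 89.4%. The stated 14 per group reproduces.
- At a 40% reduction, noncentrality = 0.511 / 0.1785 = 2.86, giving 68.5%.

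**2. ANCOVA against change score.** With s² the log variance at each time:
- Var(change) = 2s²(1 − ρ)
- Var(ANCOVA residual) = s²(1 − ρ²)
- Ratio = (1 + ρ)/2

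Two costs are charged to ANCOVA: df falls from 26 to 25, and the expected penalty for chance baseline imbalance multiplies the variance by 1 + 1/(2n − 4) = 25/24, about 4%. Equivalent n is 14 / [(1 + ρ)/2 × 25/24].

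| | Planned | ρ = 0.3 | 0.5 | 0.7 | 0.9 |
|---|---|---|---|---|---|
| Variance ratio, before penalty | 1 | 0.65 | 0.75 | 0.85 | 0.95 |
| Power, 50% reduction | 92.6% | 98.7% | 97.3% | 95.3% | 92.8% |
| Power, 40% reduction | 68.5% | 85.5% | 79.7% | 74.0% | 68.8% |
| CI width, log scale, relative | 1 | 0.82 | 0.89 | 0.94 | 1.00 |
| Equivalent patients per arm | 14 | 20.7 | 17.9 | 15.8 | 14.1 |

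Break-even is at ρ = 0.91. Simulation agrees: 98.7, 97.4, 95.2 and 92.8% at the 50% reduction (40,000 trials per setting), and 85.3, 80.5, 74.2 and 68.4% at 40% (20,000 per setting). Simulated type I error at ρ = 0.5 is 0.025 for both methods.

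**3. Unequal variances.** With λ = 6-month log SD / baseline log SD, the variance ratio is λ²(1 − ρ²) / (1 + λ² − 2ρλ). Holding the log-ratio SD at 0.472, power at a 40% reduction (planned 68.5%) is:

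| λ | ρ = 0.3 | 0.5 | 0.7 | 0.9 |
|---|---|---|---|---|
| 0.8 | 93.5% | 89.9% | 86.8% | 87.9% |
| 1.25 | 77.7% | 71.7% | 67.2% | 68.8% |

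**4. Worst case.** If the true slope is exactly 1, the variance ratio is 1 and ANCOVA only pays its two costs: 91.4% against 92.6% at a 50% reduction, and 66.3% against 68.5% at 40%.

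**The case against.** The strongest reply is that nothing in the plan is wrong. The change-score analysis is unbiased under randomization, holds its type I error, and has adequate power at the only effect the protocol gives. There the gain is 0.2 to 6 points. The larger gains need a 40% reduction that no section proposes and a correlation that no section supplies. All of this stands, and it is why the point is about efficiency and not error.

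The equal-variance condition also matters. If the 6-month log SD is 1.25 times the baseline one, the gain at ρ = 0.5 and a 40% reduction falls from about 11 points to about 3. Break-even drops to about ρ = 0.63, and at ρ = 0.7 ANCOVA is about 1 point below the plan. A ratio of 0.8 moves the result the other way. The worst case in step 4 bounds the loss whatever the ratio.

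The figures cover FDG-PET only. The documents give no variability, effect size or power for erythropoietin, and with three time points the two-time-point equivalence does not apply to it. Its repeated measures ANOVA is too loosely specified to exclude every form of baseline handling, though none is stated. The argument for adjustment carries over; its size there is not quantified.

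None of this is a reason to leave the plan as it is, because the possible loss is small and bounded.

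**Conclusion.** The concern holds as a matter of efficiency. The plan uses unadjusted change scores although a legitimate baseline covariate is already collected before randomization. For FDG-PET at 14 per arm with equal log variances, ANCOVA narrows the confidence interval by about 18% at ρ = 0.3, 11% at 0.5, 6% at 0.7 and essentially nothing at 0.9. At the planned 50% reduction the benefit is mainly that narrower interval. At an assumed 40% reduction it is worth up to 17 power points (85.5% against 68.5%). The most it can cost in these two cases is about 2 points.

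This rests on an assumed ρ, an assumed 40% alternative, two-sided alpha of 0.025, and the protocol's 50% coefficient of variation. The change should be made, but the trial is not unsound without it.

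**What to change.** In Section G, a. Analysis Plan:

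- Name as the primary analysis of each co-primary an ANCOVA of ln(6-month value) on arm and ln(baseline). Report the between-arm geometric mean ratio with its confidence interval. Define baseline as the value taken before the first open-label dose.
- For the all-visits comparison of markers with several post-randomization visits, including erythropoietin, use a mixed model with ln(baseline) as covariate (untransformed baseline for markers not analysed on the log scale). Run-in measurements precede randomization and should not enter as outcomes.
- Keep the log-ratio t-test as a sensitivity analysis.
- Add no further covariates unless the subclass and severity factors mentioned under Randomization scheme are first defined and kept to very few degrees of freedom.

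Add a sentence in Section C that the t-test calculation is retained as the sizing basis for the ANCOVA. Make the change before unblinding, so that it cannot look data-driven.

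The cost is wording only, with no new patients, visits or assays. Statistically it is one degree of freedom (26 to 25 for two arms, 39 to 38 for three arms of 14) and, in the two-arm model, an expected variance penalty of about 4%. Both are included in the two-arm figures above.
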